As a preliminary step toward designing a future study to assess the clinical benefits of the Tele-TC platform as a training system, we herein propose to assess:

- If the system enables monitoring longitudinally of adherence, proficiency, and safety;

- If the system is acceptable and user-friendly for its intended use in the home setting;
- As an exploratory aim, if a 12-week training program using the Tele-TC platform leads to improvements in balance, physical activity, self-efficacy, health-related quality of life, and gait.

If this preliminary study leads to positive results, we will embark on a follow-up study to assess the potential clinical benefits of using the technology as part of a clinical intervention on balance, physical activity, self-efficacy, health-related quality of life, and gait.

II. SPECIFIC AIMS

The overall goal of the study is to test the delivery of a novel Tele-Tai Chi (TC) intervention in a single-arm feasibility study for community-dwelling TC-naïve older adults (N=30 total). We will assess feasibility and acceptability measures of the Tele-TC intervention and its specific components through both qualitative and quantitative feedback, as well as the systematic tracking of adherence data to inform future trials and potential clinical use of the Tele-TC system. We will also explore changes in clinically relevant outcome measures including physical activity, self-efficacy, quality of life, balance, gait, and evaluate changes in TC proficiency.

We will pursue the following specific aims:

Primary aims

Aim 1: *To evaluate the feasibility, acceptability, and safety of a novel home-based Tele-TC intervention by tracking recruitment, retention, adherence, and adverse events.*

Hypothesis 1: We will be able to recruit 30 older adults and limit withdrawals to 20% or less.

Hypothesis 2: Participants will complete >60% of recommended Tele-TC sessions.

Hypothesis 3: Protocols for assessing safety can be developed and reliably administered, and preliminary evidence will support Tele-TC can be delivered safely.

Exploratory aims

Aim 2: *To evaluate changes in the level of proficiency of TC during a 12-week simplified TC program using the Tele-TC platform at home.*

Hypothesis 1: We will be able to collect reliable data on TC proficiency during Tele-TC use by study participants.

Hypothesis 2: Proficiency scores will improve over 12 weeks of training using the Tele-TC program.

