Aim 3: *To gather feedback from end-users on ease of use of the Tele-TC platform.* We plan to collect feedback from elderly subjects to assess if the system is user-friendly enough to envision its use in a clinical setting.

Hypothesis 1: We will be able to collect reliable data on ease of use of the platform using qualitative and quantitative measures.

Figure 1: Study system.

Aim 4: *To explore changes in clinically relevant outcome measures including physical activity, self-efficacy, quality of life, balance, and gait.*

Hypothesis 1: We will be able to collect reliable outcomes data at each testing visit.

Hypothesis 2: We will see clinically relevant changes in outcomes measures at 12 weeks.

III. SUBJECT SELECTION

As a preliminary test of our platform's suitability as a home-based TC program, we will recruit a convenience sample of 30 community-dwelling TC-naïve older adults into a single-arm longitudinal study of home-based TC learning, combined with remote and/or in-person data collections. In-person data collection will take place at the Spaulding Rehabilitation Hospital Motion Analysis Laboratory.

Inclusion criteria:

Eligibility criteria are purposefully broad to maximize generalizability of the study results. To be eligible to participate in the study, individuals will have to meet the following criteria:

- Men and women between 60 and 85 years old
- TC naïve (never practiced TC)
- Self-reported ability to walk continuously for 15 minutes without an assistive device
- Working email address
- Prior experience with and current access to a computer, smart phone or tablet device

Exclusion criteria:

Individuals will not be eligible to participate in the study if they exhibit any of the following:

- Chronic neuromuscular conditions (e.g. Parkinson's disease, multiple sclerosis, stroke)
- Acute medical conditions requiring hospitalization within the past 6 months or that could interfere with the safely participation in the study
- Active cancer
- Significant musculoskeletal conditions requiring chronic use of pain medication
- Cognitive impairment (Diagnosed with dementia (self-reported), or Montreal Cognitive Assessment (MoCA)-Blind score < 18)

All subjects will be recruited by IRB approved study staff for this protocol. Recruitment strategies will include the use of the following sources:

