- *PROMIS® (Patient-Reported Outcomes Measurement Information System) 29 (PROMIS-29)* instrument: 29-item questionnaire assessing each of the following domains: anxiety, depression, fatigue, physical function, pain interference, pain intensity, sleep disturbance, and ability to participate in social roles and activities. The instrument contains four items from each primary domain plus a single pain intensity rating.
- *Physical Activity Scale for the Elderly (PASE)*: self-reported level of physical activity in individuals aged 65 years or older during the previous 7 days.
- *Exercise Self-efficacy Questionnaire (SEE)*: A 9-item questionnaire that focuses on the self-efficacy expectations for exercise for older adults; specifically, the ability to continue to exercise despite barriers.

Clinical assessments which take around 15 minutes will include tests such as:

- *Camera recorded Trail Making Test A/B*: Executive function will be assessed using the Trail Making Test. Participants will be timed while sequentially connecting a series of

numbered circles (part A), as well as connecting an alternating series of numbers and letters (part B). The adjusted trail making score (i.e., part B minus A, sec) is sensitive to changes in executive function and frontal lobe pathology in older adults.

- *Instrumented and camera-recorded monitoring of balance in each leg separately.*
- *Instrumented and camera-recorded Timed-Up-and-Go:* Subjects will be asked to stand up from a chair, walk at their normal speed around a cone, turn around, and come back to sit in the chair.
- *Instrumented and camera-recorded Timed-Up-and-Go dual task:* Subjects will be asked to complete the previous task while counting backwards by three.
- *Instrumented and camera-recorded Sit-to-Stand:* Subjects will be asked to stand up from a chair while keeping their arms crossed across their chest during 30 seconds.
- *Instrumented and camera-recorded monitoring of balance in both legs* with feet shoulder-width apart and as close as possible without touching.
- *Instrumented and camera-recorded monitoring of gait.*

Instrumented and camera-recorded monitoring of TC performance will be performed during Visits #1B, #2, #3 and #4:

- Participants will be instrumented with 5 sensors (one on each limb and one on the trunk) and they will be following the instructions from the Tele-TC platform.

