The subjects will be asked to return the devices (mobile devices, sensors, tablet stands) in a prepaid and addressed box by mail after the completion of the study. The final payment for the study (\$50) will be contingent on the return of the study equipment. Those that come into the lab for their final testing visit will be asked to return the devices in person.

VI. BIOSTATISTICAL ANALYSIS

The primary outcomes of the study are the retention and the protocol adherence during the study, and the System Usability Scale collected post-intervention.

The exploratory outcomes will include the following:

- The ease of use of the Tele-Tai Chi platform measure with the qualitative interview collected post intervention.
- The changes in outcomes collected at baseline and post-intervention: the Activities-specific Balance Confidence (ABC) scores, PROMIS 29 scores, the Physical Activity Scale for the Elderly (PASE), the Trail Making Test A/B scores, Self-Efficacy Exercise (SEE) scores, the Timed-Up-and-Go, the Timed-Up-and-Go dual task single leg stance, the Sit-to-Stand performance, the balance on both legs with feet shoulder-width apart, the balance on both legs with feet close to each other, the normalized-to-height stride length and stride time variability, the activity level, and the Mini-Balance Evaluation Systems Test (MiniBEST) collected only in individuals who are willing to be tested in the MAL
- The changes in The Tai Chi proficiency scores collected at baseline, 4 weeks, 8 weeks, and pos-intervention.

Descriptive statistics will be derived for all the above-described clinical assessment outcomes and correlations will be sought with the sensor-based estimates of the metrics of adherence, proficiency and safety derived using the previously developed algorithms. Exploratory statistical analyses will be performed to power future clinical studies aimed to test the relationship between the proposed metrics of adherence and proficiency and the clinical outcomes of the intervention. Whereas conclusive statistical analyses to explore such correlations are beyond the scope of the proposed project, the data collected in this pilot study are expected to provide justification for a future trial aimed to assess the efficacy of the Tele-TC Platform as a training system.

VII. RISKS AND DISCOMFORTS

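### Do the exploratory sensor–outcome correlations in Section VI need a planned interval, given 24 to 30 people and some 45 pairs?

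*Combined protocol and SAP*

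**What the plan says.** Section VI (Biostatistical Analysis) makes retention, protocol adherence and the System Usability Scale the primary outcomes. Baseline-to-post changes in the clinical measures are exploratory. For those measures it plans descriptive statistics and adds that "correlations will be sought with the sensor-based estimates of the metrics of adherence, proficiency and safety derived using the previously developed algorithms". The next sentence gives the work a forward-looking purpose: "Exploratory statistical analyses will be performed to power future clinical studies aimed to test the relationship between the proposed metrics of adherence and proficiency" on one side and clinical results on the other. The sentence after that limits it: "Whereas conclusive statistical analyses to explore such correlations are beyond the scope of the proposed project".

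The section names no interval or other precision measure, no correlation method and no number of pairs. The MiniBEST is "collected only in individuals who are willing to be tested in the MAL", so it will be available in an unstated subset.

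Section III (Subject Selection) says "we will recruit a convenience sample of 30 community-dwelling TC-naïve older adults into a single-arm longitudinal study", and gives no derivation of that number. Section II (Specific Aims), Aim 1, sets the feasibility target: "We will be able to recruit 30 older adults and limit withdrawals to 20% or less".

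**The concern.** A stated aim of powering later studies suggests that the pilot's correlations may be used as planning values. A correlation from 24 to 30 people is a poor planning value, and many are to be computed. Printed without intervals, the table would not show which entries are compatible with zero. Its largest entries could be mistaken for signals when chance alone produces values of that size. A follow-up study sized on such a value could be far too small.

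**Working it through.** **Nothing to reproduce.** N=30 is a convenience sample with no stated alpha, power, target correlation or precision.

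**Inputs from the protocol**
- Recruited: 30 (Section III).
- Remaining at the withdrawal ceiling: 30 × (1 − 0.20) = 24 (Section II).
- Metrics: three in the correlation sentence (adherence, proficiency, safety); two in the powering sentence (adherence, proficiency).
- Outcomes, my count from Section VI: ABC, PROMIS-29 as one, PASE, Trail Making, SEE, Timed-Up-and-Go, its dual-task form, single leg stance, Sit-to-Stand, two two-leg balance tests, stride length, stride time variability, activity level and MiniBEST, so 15.
- Pairs: 15 × 3 = 45, or 15 × 2 = 30 for the powering sentence alone. Section V lists eight PROMIS-29 scores; counted separately they give 15 − 1 + 8 = 22 outcomes and 22 × 3 = 66 pairs.

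**Assumed, not in the protocol:** the values of r, one score per person per metric, roughly bivariate-normal data, the inter-correlations, and 80% power at two-sided 5% for a later study.

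**Precision of one correlation.** 95% CI = tanh(atanh(r) ± 1.96/√(n − 3)). The smallest |r| whose interval excludes zero is tanh(1.96/√(n − 3)):
- n=24: tanh(1.96/√21) = 0.403
- n=30: tanh(1.96/√27) = 0.360

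| Observed r | n=24 | n=30 |
|---|---|---|
| 0.30 | −0.12 to 0.63 | −0.07 to 0.60 |
| 0.40 | −0.00 to 0.69 | 0.05 to 0.67 |
| 0.50 | 0.12 to 0.75 | 0.17 to 0.73 |

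For MiniBEST, if half of 24 attended the lab (n=12, assumed), an observed 0.30 would have an interval of −0.33 to 0.75.

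**If an observed value were used for sizing.** N = ((1.96 + 0.8416)/atanh(r))² + 3. An r of 0.50 gives 30 people. Its interval limits give 12 to 534 (pilot n=24) or 13 to 268 (pilot n=30). For an observed 0.30 the interval includes zero, so there is no upper limit.

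**Largest |r| with no true association.** Simulated with normal data, 6,000 sets per setting, and the same inter-correlation within metrics and within outcomes. Median of the largest |r|:

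| Pairs | Inter-correlation | n=24 | n=30 |
|---|---|---|---|
| 30 | 0 | 0.460 | 0.413 |
| 30 | 0.5 | 0.424 | 0.375 |
| 30 | 0.7 | 0.377 | 0.334 |
| 45 | 0 | 0.490 | 0.439 |
| 45 | 0.5 | 0.452 | 0.402 |
| 45 | 0.7 | 0.404 | 0.359 |
| 66 | 0 | 0.512 | 0.461 |
| 66 | 0.5 | 0.471 | 0.423 |
| 66 | 0.7 | 0.425 | 0.372 |

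At 45 pairs, the chance that the largest |r| passes 0.4 falls from 0.92 (independent) to 0.52 (inter-correlation 0.7) at n=24, and from 0.73 to 0.34 at n=30.

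**Intervals excluding zero by chance.** With 45 pairs the expected number is 45 × 0.05 = 2.25. The chance of at least one is 1 − 0.95^45 = 0.90 if the pairs are independent, and about 0.70 at an inter-correlation of 0.5.

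**What in the plan uses these values.** The primary outcomes do not use them. Section VI has no threshold, no rule for picking a pair and no formula for sizing a later study. The powering sentence does not say which exploratory analyses it means; variability, adherence distributions and the four-visit proficiency scores could also inform power.

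**The case for a change.** The best case for a change is that the caveat in Section VI concerns conclusiveness, while the sentence before it gives the same analyses a planning use, and the caveat's own sentence expects the data to justify a future trial. A general disclaimer does not tell a reader which correlations are compatible with zero, or that a largest value near 0.45 is ordinary chance at this size. Two sentences and one table would show it, with no new data and no burden on participants.

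The arithmetic stands, and so does the reporting advice: an interval and an n beside each correlation, with the number of pairs stated, is good practice. The need to amend the plan does not stand. Nothing in the protocol prevents that reporting, and a statistician would normally supply it. The harm arises only if someone selects the largest correlation and sizes a study on it, which the protocol does not propose.

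A stronger rule, that the intervals be read as planning ranges and that an interval including zero leaves a future study's size unbounded, would be debatable in itself. It ties sizing to noisy pilot estimates, whereas a later study can be sized on the smallest relationship worth detecting. Fixing a Fisher z interval now would also be premature: MiniBEST items are ordinal, adherence may be bounded, and no summary of the repeated proficiency scores has been chosen.

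**Conclusion.** No change is needed. The correlations will be imprecise: an interval includes zero unless |r| exceeds about 0.40 (n=24) or 0.36 (n=30). The median largest value under no association is 0.33 to 0.51 over 30 to 66 pairs and inter-correlations of 0 to 0.7. A typical maximum of 0.4 to 0.5 is therefore likely under weak inter-correlation but not assured, since several balance and gait measures overlap in content. These figures rest on my count of outcomes, one score per metric, near-normal data and assumed inter-correlations. The qualitative point holds at 30, 45 or 66 pairs.

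The missing interval is a reporting detail in a short pilot section that already labels the work exploratory and not conclusive. It alters no primary outcome, no decision rule and no conclusion the pilot is designed to reach. Analysts can fill it at the reporting stage by giving n and a 95% interval for each correlation and stating how many pairs were examined. Intervals would show the imprecision but would not reduce it.

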When subjects first contact the study team, a member of the study team will provide them with a detailed description of the study over the phone or in person. If interested and deemed potentially eligible, a member of the study team will offer to send the informed consent form to the subject. Subjects will be encouraged to call study staff with any questions or concerns they might have prior to their first study visit. Consent will be obtained remotely using the eConsent process on REDcap by a trained research staff member designated by the Principal Investigator as adequately knowledgeable of the risks/benefits of the study and the vulnerability of the study population and capable to critically assess the subject's awareness of these factors. The subject will be encouraged to continue to ask questions and express concerns - if any - to study staff throughout their participation in the study. Enrollment will begin when it is clear that the subject thoroughly understands and e-signs the informed consent form. Testing will only take place once the informed consent form is signed.

V. STUDY PROCEDURES

The study procedures will be carried out remotely using a Zoom Enterprise Partners account or in person.

Eligible subjects will undergo the informed consent process in person, by phone or on Zoom Enterprise with a trained research assistant at the beginning of the baseline testing visit. Once consented, subjects will undergo baseline assessments (visit #1) in person or remotely using Zoom Enterprise and REDcap Survey. After baseline testing, subjects will participate in the Tele-TC intervention, with recommended training sessions at least three times a week, along with two or more supplementary one-on-one live sessions (lasting upwards to 45 minutes) with TC instructors. TC proficiency using wearable sensors will be assessed at visit #1 baseline, at two follow-up assessments (visit #2 and visit #3) at approximately 4 and 8 weeks, and at a final assessment (visit #4) at 12 weeks. A semi-structured qualitative interview will also be performed at visit #1 and #4.

[figure not shown]

Figure 2: Flow Chart of the study.

Below, we provide a detailed description of the study procedures.

1. Remote Screening and Informed Consent (Visit #1A)

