TC is likely to be safe, as there have been no reports of serious adverse impacts in the TC literature. We experienced no serious adverse events in our pilot studies with COPD, heart failure, vestibulopathy, and osteopenic populations. However, there may be some potential expected risks to participants including the following:

1. TC and other motor tasks included in the clinical evaluations of balance and gait may cause some muscle soreness in highly deconditioned individuals. This soreness is likely to only last a short time. In addition, shortness of breath, dizziness, or falls are possible. However, these risks are unlikely and will be discussed in both the protocol and consent form.
2. Possible discomforts associated with using the sensors are the same as those experienced when wearing other wearable devices such as bracelets, watches and heart monitor straps. Prolonged use of the sensors may cause sweating and skin irritation.

There is a possibility that subjects could fall or trip during the experimental procedures, or that they may experience an allergic reaction or minor skin irritation to the band used to attach the

sensors to the body. There is also a possibility that subjects may become fatigued or experience muscle soreness.

The risk of falling during the TC exercises and balance tests will be minimized by excluding subjects with balance impairments and risk of falls based on medical history, self-reported previous falls, and some clinical tests to assess potential balance impairments in study participants, whose outcome will be used by a rehabilitation specialist to determine if the subject can safely perform the TC exercises. If a subject falls during remote visits or TC practice, they will be referred to their physician or to urgent care as needed.

Fatigue and muscle soreness will be minimized by allowing subjects to rest at any point during the experimental procedures.

Subjects will be encouraged to contact MAL staff with any questions or concerns they may have at any time during the study or after its completion.

Overall, the potential risks to participants are modest and are likely to be viewed as reasonable in relation to the anticipated benefits to subjects and others.

Safety

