When - according to a rehabilitation specialist during in-person testing, or research staff during virtual testing - subjects are unable to safely perform the TC exercises that are part of the experimental procedures, the experiment will end. Subjects will be told why the experiment must stop and will be advised to seek medical care if appropriate.

Subjects will be told that the study procedures may be associated with discomfort due to wearing the sensors and by fatigue/muscle soreness. In case subjects experience discomfort or excessive fatigue, they will be free to remove the sensors and end their participation in the study.

Foreseeable Risks and Discomfort

Unintentional loss/disclosure of Protected Health Information may occur and is considered a minimal risk due to the security measures enforced at SRH. Confidential information will be kept in a locked filing cabinet, on REDcap, and on password-protected computers in the MAL.

VIII. POTENTIAL BENEFITS

Study participants are not expected to directly benefit from their participation, but it is possible that subjects will experience some positive impact on physical and mental health as a result of their performing TC exercises, as has been shown in prior TC studies. Information gained during the study is expected to contribute to the development of systems to facilitate the deployment of TC-based interventions.

IX. MONITORING AND QUALITY ASSURANCE

Because this study's procedures pose minimal risk to the subjects, bimonthly data and procedural reviews by the PI in consultation with study staff will be sufficient to identify and ameliorate any

potential safety issues. Any safety concerns about the equipment or testing protocol will be brought to the immediate attention of [name]. Study staff will conduct bimonthly audits to ensure compliance with regulatory requirements for study documentation.

Approval of protocol, informed consent procedures, and recruitment will be obtained from the IRB during annual reviews.

Adverse event reporting will be done according to Partners Human Research Policy. Remedial action to prevent reoccurrence of the event will be instituted prior to the resumption of study procedures.

Study staff will conduct quarterly audits to ensure compliance with regulatory standards for study documentation.

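### Section VII relies on excluding people with balance impairment or fall risk, but none of the ten eligibility criteria in Section III mentions balance or falls

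*Combined protocol and SAP*

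**What the plan says.** Section VII (Risks and Discomforts) names the control for falls during the Tai Chi exercises and balance tests: "excluding subjects with balance impairments and risk of falls based on medical history, self-reported previous falls, and some clinical tests". The tests are ones "whose outcome will be used by a rehabilitation specialist to determine if the subject can safely perform the TC exercises".

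Section III (Subject Selection) opens its exclusion list with "Individuals will not be eligible to participate in the study if they exhibit any of the following" and describes the eligibility criteria as deliberately wide so that results generalise. Neither list has an entry on balance, fall risk or previous falls. One exclusion does use a test score, "Montreal Cognitive Assessment (MoCA)-Blind score < 18", but the section does not say when that test is given.

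Section IV (Subject Enrollment) sends the consent form to people who are "If interested and deemed potentially eligible", starts enrollment at e-signature, and adds: "Testing will only take place once the informed consent form is signed". Section V.1 has staff confirm eligibility with a short questionnaire before consent, on top of the phone screen. Section V.2 places the balance, Timed-Up-and-Go, Sit-to-Stand and gait tests at Visits #1B and #4. Section VI uses them as exploratory outcomes.

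The Safety text in Section VII adds a stop rule: if "subjects are unable to safely perform the TC exercises that are part of the experimental procedures, the experiment will end". That is judged "according to a rehabilitation specialist during in-person testing, or research staff during virtual testing".

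**The concern.** The exclusion is the specific measure that Section VII offers against falling. A person with repeated falls or poor balance, but none of the listed diagnoses, meets every criterion in Section III. Staff working from that list would enrol someone whom Section VII says is excluded.

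Two things are at stake:

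- **Participant safety.** Most exposure to the exercises is home practice. Section V.3 asks for at least 3 days a week over 12 weeks, so 3 × 12 = 36 sessions or more, of 45 to 60 minutes each. A decision made before that practice begins is the one left undefined.
- **Meaning of the safety evidence.** Aim 1, Hypothesis 3 seeks preliminary evidence that the programme can be delivered safely. A given number of falls among 30 people reads differently if those at risk were screened out than if they were admitted. The study is meant to inform future trials of a platform titled for fall prevention, so readers will need to know which population it describes.

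**Working it through.** The plan gives no figure on this point, so the check is a count and a comparison of sections.

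1. **Inclusion criteria (Section III), 5 items:** age 60 to 85; no previous Tai Chi; self-reported 15-minute walk without a device; working email; experience with and access to a computer, phone or tablet. Items naming balance or falls: 0.

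2. **Exclusion criteria (Section III), 5 items:** chronic neuromuscular disease; acute illness with recent hospitalisation or interfering with safe participation; active cancer; musculoskeletal disease needing long-term pain medication; cognitive impairment. Items naming balance or falls: 0. The total is 0 of 5 + 5 = 10.

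3. **Could a listed item stand in for the exclusion?** The walking item is self-reported and concerns endurance and aids. The neuromuscular item depends on a diagnosis. The safe-participation wording is confined to acute conditions. The musculoskeletal item depends on pain medication. Each would remove some people at higher risk, but none uses previous falls or a balance test, which are bases that Section VII names.

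4. **Does Section V apply it?** The phone screen and short questionnaire are described without falls or balance content. The Visit #1B balance tests carry no cut-off and no eligibility decision. The overview in Section V passes from baseline testing to the intervention with no decision between them. The forms themselves are not reproduced and Figure 2 is not shown, so this step establishes only what the visible text says.

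5. **Could the order of events settle it?** It does not. Section V.1 confirms eligibility before consent, while Section IV allows testing only after consent. An exclusion that rests partly on clinical tests would then fall after e-signature, when enrollment has begun. Section IV's reference to potential eligibility, and the MoCA-Blind criterion with no stated time, leave room for a later decision, but no section describes one.

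6. **Does the stop rule under Safety fill the gap?** It is worded for in-person and virtual testing and ends the procedures. It is not an entry criterion and does not speak to unsupervised home practice.

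**The case against.** The best defence is that Section VII is current text of the same protocol. It states the exclusion, its basis and the role that uses the test results, so careful staff would apply it. On this view Section III is merely incomplete, and the phone screen, the questionnaire or Figure 2 may hold the step. The walking and neuromuscular criteria, chairs for stability and the stop rule give further protection. Part of this stands: the documents do not show that the exclusion would never be applied, and the partial safeguards are real. It does not remove the conflict, because Section III presents its lists as the eligibility criteria and calls them broad. A step on an unseen form would still not be in them.

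Three stronger readings are tempting, and the documents do not support them:

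- **That Section VII contradicts itself on who judges safe performance.** The risk text names a rehabilitation specialist without distinguishing visit mode, and the Safety text names research staff at virtual testing. These can be read as two decisions, one on entry and one on ending a test in progress. The wording needs clarifying, but a contradiction is not shown.
- **That fall history will not be recorded.** Section VII says previous falls are self-reported, and Section V.4 has staff ask about falls from Visit #1b, which precedes home training. History may be partly captured. Only the look-back period is missing.
- **That the retention result is affected.** The limit in Aim 1, Hypothesis 1 is 20% of 30 = 6 withdrawals, so one exclusion counted as a withdrawal would add 1/30 = 3.3 percentage points. The documents give no expected number of exclusions or other dropouts, so no change in the result can be claimed.

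**Conclusion.** The concern holds as an internal inconsistency between Sections III and VII. The protocol names an exclusion as its control for falling, and 0 of its 10 eligibility criteria contains it. The visible Section V text does not supply it either. Whether people at risk of falling may enrol is therefore not settled by the protocol as written.

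Confidence is high on the mismatch between the two sections, which rests on the text alone. It is moderate on the absence of a decision step, because that assumes the screening forms and Figure 2 contain none. The consequence is for participant safety and for the population that the Aim 1 safety evidence describes; there is no demonstrated effect on a primary outcome. It should be fixed, and the repair is inexpensive.

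**What to change.** Reconcile Sections III, IV, V and VII so that one rule, chosen and defined by the investigator, appears throughout. Which rule is right is not a question for this review.

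- **If the exclusion is intended:** list it in Section III. State in Section V when it is decided, and by which role, before home practice begins, for remote and in-person participants alike. State whether a person excluded after e-consent counts as a screen failure or as a withdrawal.
- **If it is not intended:** remove the claim from Section VII and restate the fall risk there.

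Two minor clarifications belong in the same amendment: whether the differing roles in the risk text and the Safety text refer to two separate decisions, and whether the fall inquiry at Visit #1b covers falls before enrollment.

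The cost is a short amendment. Keeping the exclusion narrows eligibility and takes some assessment time, including for remote participants. Dropping it leaves a less favourable risk statement.
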